#### **Adverse Events**

The terms used in the eCRFs by investigators to identify adverse events will be coded using the Medical Dictionary for Regulatory Activities (MedDRA). All reported adverse events with onset during the treatment phase (ie, treatment-emergent adverse events) will be included in the analysis. Additionally, a summary of all reported adverse events (regardless of whether treatment-emergent) will also be provided.

For each adverse event, the percentage of subjects who experienced at least 1 occurrence of the given event will be summarized by treatment group. The percentage of subjects with specific treatment-emergent adverse events will be summarized by severity and relationship to study drug, as classified by the investigator, by treatment group.

Special attention will be given to those subjects who died, or who discontinued treatment due to an adverse event, or who experienced a severe or a serious adverse event (eg, summaries, listings, and narrative preparation may be provided, as appropriate).

Further analyses, to be described in the SAP for this study, will be conducted on the pre-specified adverse events for which additional information is collected from the investigators (refer to Section 9.8, Safety Evaluations), and on other adverse events.

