#### 12. ADVERSE EVENT REPORTING

Timely, accurate, and complete reporting and analysis of safety information from clinical studies are crucial for the protection of subjects, investigators, and the sponsor, and are mandated by regulatory agencies worldwide. The sponsor has established Standard Operating Procedures in conformity with regulatory requirements worldwide to ensure appropriate reporting of safety information; all clinical studies conducted by the sponsor or its affiliates will be conducted in accordance with those procedures.

For adverse events of interest, investigators will be asked to provide additional information. Adverse events of interest include all malignancies, severe hypersensitivity reactions (eg, angioedema, anaphylaxis, Stevens-Johnson syndrome), photosensitivity reactions, serious adverse events of hepatic injury, nephrotoxicity/acute kidney injury, venous thromboembolic events, fractures, and pregnancy.

The following adverse events have been designated as adverse events of special interest and need to be reported to Janssen within 24 hours of becoming aware of the event, which is the same timeframe for reporting of serious adverse events. These adverse events must be reported using a supplemental reporting form, to complement standard information collected on the Adverse Event/SAE eCRF, together with the SAE report for serious events.

- Diabetic ketoacidosis and adverse events related to DKA, ketoacidosis, metabolic acidosis or acidosis
- Amputations
- Pancreatitis
- Serious adverse events of UTIs including urosepsis and pyelonephritis

Additional information and documentation will be requested from investigators to support a detailed assessment of all deaths. Investigators may also be asked to provide additional information on other adverse events, based upon review by the MSRC. If adverse events of interest are identified in the future, guidance concerning the reporting of those events may be provided to investigators via appropriately-documented study communications.

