6.1.1. Selected Adverse Events for Additional Analysis

To support the additional assessment of particular categories of AEs, such as vulvovaginal candidiasis, balanitis or balanoposthitis, urinary tract infections (UTIs), volume depletion, hepatic injury, renal impairment/renal failure, hypersensitivity, venous thromboembolic event, photosensitivity, and malignancy, groupings of selected preferred terms will be created. A blinded review prior to database lock will be performed to assure that no reported term suggestive of the AE of interest is omitted. The list of preferred terms that are to be combined for assessment of each of the pre-specified AEs is provided in Attachment 2. Given the planned sample size of the study (ie, 146 subjects overall), listings may be provided instead of summary tables for any selected AEs below that are reported with low incidence (ie, <5%).

Fracture events identified by the investigator or the sponsor for meeting the criteria pre-specified in the charter will be sent to an independent fracture adjudication committee to confirm that events were fractures, to determine fracture location (anatomic region) and type (low trauma or not). Summary of the fracture events will be based on the adjudicated events of fracture.

Diabetic ketoacidosis (DKA) identified by investigator or the sponsor for meeting the criteria prespecified in the charter will be sent to an independent DKA adjudication committee. Summary of the DKA events will be based on the adjudicated events of DKA.

Pancreatitis identified by investigator or the sponsor for meeting the criteria pre-specified in the charter will be sent to an independent pancreatitis adjudication committee. Summary of the pancreatitis events will be based on the adjudicated events of pancreatitis.

Lower extremity amputation will be recorded on a dedicated amputation case report form page. Summary of the lower extremity amputation will be based on the case report form page.

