Acute kidney injury; Acute phosphate nephropathy; Acute prerenal failure; Anuria; Azotaemia; Blood creatinine increased; Blood urea increased; Continuous haemodiafiltration; Dialysis; Glomerular filtration rate decreased; Haemodialysis; Haemofiltration; Hypercreatinaemia; Neonatal anuria; Nephritis; Nephropathy toxic; Oliguria; Peritoneal dialysis; Prerenal failure; Renal failure; Renal failure acute; Renal failure neonatal; Renal impairment; Renal impairment neonatal.

Hypersensitivity

Anaphylactic reaction; Anaphylactic shock; Anaphylactoid reaction; Anaphylactoid shock; Angioedema; Laryngeal oedema; Laryngotracheal oedema; Oropharyngeal swelling; Pharyngeal oedema; Rash; Rash erythematous; Rash generalized; Rash generalized; Rash macular; Rash maculopapular; Rash maculo-papular; Rash papular; Rash pruritic; Rash pustular; Rash vesicular; Small bowel angioedema; Swollen tongue; Tongue oedema; Urticaria.

Venous Thromboembolic Event

Deep vein thrombosis; Deep vein thrombosis postoperative; Embolism venous; Iliac vein occlusion; Inferior vena cava syndrome; Inferior vena caval occlusion; Jugular vein occlusion; Mesenteric vein thrombosis; Mesenteric venous occlusion; Obstructive shock; Portosplenomesenteric venous thrombosis; Post procedural pulmonary embolism; Postpartum venous thrombosis; Pulmonary embolism; Pulmonary infarction; Pulmonary microemboli; Pulmonary oil microembolism; Pulmonary thrombosis; Renal vein embolism; Renal vein occlusion; Subclavian vein thrombosis; Vascular occlusion; Venous thrombosis; Venous thrombosis in pregnancy; Venous thrombosis limb; Visceral venous thrombosis.

Photosensitivity

Actinic elastosis; Actinic prurigo; Administration site photosensitivity reaction; Application site photosensitivity reaction; Chronic actinic dermatitis; Hartnup disease; Implant site photosensitivity; Infusion site photosensitivity reaction; Injection site photosensitivity reaction; Juvenile spring eruption; Medical device site photosensitivity reaction; Photodermatosis; Photokeratitis; Photoonycholysis; Photosensitivity reaction; Polymorphic light eruption; Solar dermatitis; Solar urticaria; Sunburn; Vaccination site photosensitivity.

Hepatic Injury

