Acute graft versus host disease in liver; Acute hepatic failure; Acute yellow liver atrophy; Allergic hepatitis; Ammonia increased; Ascites; Asterixis; Autoimmune hepatitis; Bacterascites; Biliary ascites; Biliary cirrhosis; Biliary cirrhosis primary; Biliary fibrosis; Bilirubin excretion disorder; Biopsy liver abnormal; Child-Pugh-Turcotte score increased; Cholaemia; Cholestasis; Cholestatic liver injury; Cholestatic pruritus; Chronic graft versus host disease in liver; Chronic hepatic failure; Chronic hepatitis; Coma hepatic; Cryptogenic cirrhosis; Diabetic hepatopathy; Drug-induced liver injury; Duodenal varices; Focal nodular hyperplasia; Gallbladder varices; Gastric varices; Gastric varices haemorrhage; Graft versus host disease in liver; Haemangioma of liver; Haemorrhagic ascites; Haemorrhagic hepatic cyst; Hepatectomy; Hepatic adenoma; Hepatic atrophy; Hepatic calcification; Hepatic cirrhosis; Hepatic cyst; Hepatic cyst ruptured; Hepatic encephalopathy; Hepatic encephalopathy prophylaxis; Hepatic failure; Hepatic fibrosis; Hepatic fibrosis marker abnormal; Hepatic haemangioma rupture; Hepatic hydrothorax; Hepatic infiltration eosinophilic; Hepatic lesion; Hepatic necrosis; Hepatic steatosis; Hepatitis; Hepatitis acute; Hepatitis cholestatic; Hepatitis chronic active; Hepatitis chronic persistent; Hepatitis fulminant; Hepatitis toxic; Hepatobiliary disease; Hepatocellular foamy cell syndrome; Hepatocellular injury; Hepatopulmonary syndrome; Hepatorenal failure; Hepatorenal syndrome; Hepatotoxicity; Hyperbilirubinaemia; Icterus index increased; Intestinal varices; Ischaemic hepatitis; Jaundice;

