Benign neoplasm of testis, Leydig cell tumour of the testis, Sertoli cell testicular tumour, Spermatocytic seminoma, Testicle adenoma, Testicular cancer metastatic, Testicular neoplasm, Testicular papilloma, Testis cancer.

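### SAP Attachment 2 does not deliver three of the protocol's adverse-event-of-interest categories: all malignancies, severe hypersensitivity and serious hepatic injury

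*SAP*

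**What the plan says.** **Protocol 12 (Adverse Event Reporting)** sets the categories: "Adverse events of interest include all malignancies, severe hypersensitivity reactions (eg, angioedema, anaphylaxis, Stevens-Johnson syndrome), photosensitivity reactions, serious adverse events of hepatic injury". The list goes on to kidney injury, venous thromboembolism, fractures and pregnancy. Investigators must supply additional information on these events.

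**Protocol 11.6 (Safety Analyses, Adverse Events)** passes the analysis on: "Further analyses, to be described in the SAP for this study, will be conducted on the pre-specified adverse events for which additional information is collected".

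**SAP 6.1.1** takes up that role. It says "hepatic injury, renal impairment/renal failure, hypersensitivity, venous thromboembolic event, photosensitivity, and malignancy, groupings of selected preferred terms will be created", and then "The list of preferred terms that are to be combined for assessment of each of the pre-specified AEs is provided in Attachment 2". It states no severity condition for hypersensitivity and no seriousness condition for hepatic injury. A blinded review before database lock is planned "to assure that no reported term suggestive of the AE of interest is omitted".

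**SAP Attachment 2** gives the lists:
- Hypersensitivity includes "Pharyngeal oedema; Rash; Rash erythematous; Rash generalized", further rash terms and Urticaria, alongside anaphylactic and angioedema terms.
- Hepatic injury includes "Hepatic necrosis; Hepatic steatosis; Hepatitis; Hepatitis acute", and also Non-alcoholic steatohepatitis, Hepatic cyst, Haemangioma of liver and Hepatic adenoma.
- Malignancy has five headings: renal cell, bladder, phaeochromocytoma, breast and testicular. The testicular list opens "Benign neoplasm of testis, Leydig cell tumour of the testis" and also contains Testicle adenoma and Testicular papilloma.

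**The concern.** Overall safety and tolerability is one of the two primary objectives (Protocol 2.1). The selected-AE groupings are where a reader of the study report will look for the events that the protocol singled out. If a row labelled hypersensitivity counts every new rash, it does not answer the protocol's question about severe reactions. If a row labelled malignancy counts a benign tumour but has no place for a leukaemia or lymphoma, its label is wrong in both directions. Deciding which terms qualify only after the reported terms are seen, even blinded, is weaker than a rule fixed in the attachment.

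**Working it through.** The plan gives no figure to reproduce; this is a comparison of definitions, followed by a count and one illustration.

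**1. Category by category**

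| Category | Protocol 12 | SAP 6.1.1 and Attachment 2 | Difference |
|---|---|---|---|
| Malignancy | all | five tumour types; benign testicular terms included | too narrow by site, too broad by behaviour |
| Hypersensitivity | severe; three examples named | any severity; Stevens-Johnson syndrome not listed | too broad, with one named example missing |
| Hepatic injury | serious adverse events only | serious or not | too broad only; the protocol names no specific hepatic term |

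Other protocol categories are not at issue. Photosensitivity, renal and thromboembolic events have lists. SAP 6.1.1 sends fractures, ketoacidosis and pancreatitis to adjudication and takes amputations from a dedicated form.

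**2. Counting the lists**
- Hypersensitivity: 24 entries, 23 distinct strings. Eleven entries (10 distinct) begin with Rash; none is Stevens-Johnson syndrome. The list is alphabetical, and that term would fall between Small bowel angioedema and Swollen tongue, which stand next to each other. A loss in text conversion is therefore unlikely.
- Testicular: 9 entries, of which 3 (Benign neoplasm of testis, Testicle adenoma, Testicular papilloma) are benign by name.

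**3. Applying both rules to example treatment-emergent records**

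| Record | Protocol 12 | Attachment 2 as written |
|---|---|---|
| Mild Rash macular | not of interest | hypersensitivity |
| Stevens-Johnson syndrome | of interest | in no list unless the review adds it |
| New, non-serious Hepatic steatosis | not of interest | hepatic injury |
| Acute leukaemia | of interest | in no list unless the review adds it |
| Testicle adenoma | not a malignancy | malignancy |

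**4. Can the breadth change the output?** SAP 6.1.1 allows a listing in place of a table for selected AEs below 5% incidence. Taking incidence over all 146 subjects, 0.05 × 146 = 7.3, so the boundary lies between 7 subjects (7/146 = 4.8%) and 8 (8/146 = 5.5%). With X ~ Binomial(146, p), the chance of 8 or more subjects is:

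| Assumed rate p | P(X ≥ 8) |
|---|---|
| 0.2% | below 0.0001 |
| 0.5% | below 0.0001 |
| 1% | 0.0001 |
| 3% | 0.07 |
| 5% | 0.45 |
| 8% | 0.91 |

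The first three rows stand for severe reactions only and the last three for a broad list containing rash. At 3% to 8% the expected count is 146 × 0.03 = 4.4 to 146 × 0.08 = 11.7 subjects. All these rates are assumptions; the documents give none. The illustration shows only that rash could decide whether the category is tabulated.

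**The case against.** The strongest reply is that the two lists do different jobs. Protocol 12 triggers extra data collection. SAP 6.1.1 pools terms for a sensitive search and includes categories outside the protocol's list, such as candidiasis and volume depletion. Protocol 11.6 does not require identical definitions. A broad pool is legitimate, and that part stands, so the broad lists should stay. It does not explain why the categories that Protocol 11.6 sends to the SAP have no row of their own, or why benign terms sit under a malignancy heading.

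Four stronger readings are tempting, and the documents do not support them:

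- **That events would be hidden or lost.** SAP 6.1 tabulates every adverse event by preferred term and by severity, and lists deaths, SAEs and events leading to discontinuation. A severe rash, serious liver event, Stevens-Johnson case or leukaemia would be visible there.
- **That the hepatic row would fill with pre-existing fatty liver.** Amendment 4 says fatty liver is not uncommon in this population, and the ALT exclusion starts only above 5 times ULN. But SAP 6.1 counts an event as treatment-emergent only with onset after the first double-blind dose, or with later worsening or changed attribution. Known significant liver disease is excluded, the hepatic list holds no raised-ALT or raised-AST term, and enzymes are handled separately in SAP Attachment 4.
- **That omitted terms would stay omitted.** The blinded review exists for that case, and SAP 6.1.1 names malignancy without a site limit. What the review lacks is any stated rule for taking out benign, non-severe or non-serious terms; its text neither provides for removal nor forbids it.
- **That the tumour sites are arbitrary.** Protocol 1.1.3 reports rat renal tubular cancers, Leydig cell tumours and phaeochromocytomas. That explains three of the five groups, and a testicular group wider than cancer. It is a reason to keep benign testicular terms under observation, not to label them malignant.

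SAP 6 also plans no hypothesis testing for safety, so no formal conclusion depends on these rows.

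**Conclusion.** The mismatch is in the text and needs no assumption. As written, Attachment 2 counts three benign testicular terms as malignancy and covers five tumour types where the protocol says all. It omits one named severe reaction and gives no pooled row for severe hypersensitivity or serious hepatic injury. For hepatic injury the fault is over-breadth alone.

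The effect is limited to the selected-AE summaries. Efficacy, error control and the general safety tables are untouched, and the omissions can be repaired at the blinded review. The rash rates in the illustration are assumed and the conclusion does not rest on them. The point is worth correcting because the label and content of these rows disagree on a primary objective and the correction costs almost nothing.

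**What to change.** Amend SAP 6.1.1 and Attachment 2 before database lock. Keep the broad lists and add three protocol-defined rows:

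1. **Severe hypersensitivity**, with Stevens-Johnson syndrome and related severe cutaneous terms added to the list.
2. **Serious hepatic injury**, restricted to serious adverse events.
3. **All malignant neoplasms**, any site.

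Show benign testicular tumours in a separately labelled testicular-tumour group and not under malignancy, so that surveillance of the preclinical signal is kept.

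The cost is an attachment edit and three more table or listing rows. Severity, seriousness and coded terms are already collected, and Protocol 12.2.1 already provides a supplemental form for events of interest.

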Attachment 3: Clinical Laboratory Tests

The clinical laboratory tests include following panels and assessments:

- Hematology panel
 - hemoglobin
 - platelet count
 - hematocrit
 - o red blood cell (RBC) count
 - white blood cell (WBC) count with differential
- Serum chemistry panel
 - \circ sodium
 - o potassium
 - o chloride
 - o bicarbonate
 - blood urea nitrogen (BUN)
 - \circ creatinine

total bilirubin

- aspartate aminotransferase (AST)
- alanine aminotransferase (ALT)
- o gamma-glutamyltransferase (GGT)

- o alkaline phosphatase
- o creatine phosphokinase (CPK)
- lactic acid dehydrogenase (LDH)
- o uric acid
- o calcium
- o phosphate
- o albumin
- o total protein
- o magnesium
- Fasting serum lipid profile (low-density lipoprotein-cholesterol [LDL-C], high-density lipoprotein-cholesterol [HDL-C], total cholesterol, non-HDL-C, LDL-C to HDL-C ratio, non-HDL-C to LDL-C ratio, and triglycerides)
- HbA_{1c}
- FPG
- C-peptide (random and fasting)

0

- Blood ketones
- Bone turnover markers (serum osteocalcin and serum collagen type 1 carboxy-telopeptide [CTx])
- Markers of calcium and phosphate homeostasis (calcium, magnesium, phosphate, PTH, 25-hydroxy Vitamin D, calcitonin; urinary excretion of calcium and phosphate)
- Urinalysis

Dipstick done at central laboratory -specific gravity -pH -glucose -protein -blood -ketones -bilirubin -urobilinogen -nitrite -leukocyte esterase

If dipstick result is abnormal, microscopic examination will be performed.

• First morning void urine for Urinary ACR

Subject who have a Week -2 first morning void showing a presence with proteinuria (ie, proteinuria +1 and above) based on the central laboratory urine dipstick, will require a 24-hour urine collection prior to randomization and thereafter.

- Serum (β-human chorionic gonadotropin [β-hCG] pregnancy testing will be conducted for all female subjects of childbearing potential at screening visit. Additional urine (or serum) pregnancy tests may be performed, as determined necessary by the investigator, or required by local regulation, to establish the absence of pregnancy at any time during the study.
- Testing for pancreatic autoimmunity (GAD and islet cell antigen 2 [IA2] antibody) will be conducted in subjects with no available documentation at time of screening.
- Subjects must be fasting for at least 8 hours before collection of blood samples that require fasting (eg, glucose, lipid panel, etc).

Central laboratory will report the estimated glomerular filtration rate (eGFR) at study visits when serum creatinine is measured as specified below:

- Estimated Glomerular Filtration Rate (eGFR)
 - eGFR will be calculated using Schwartz formula:
 - eGFR $(mL/min/1.73 \text{ m}^2) = (0.55 \times \text{height in cm}) / \text{serum creatinine in mg/dL for}$ girls from 10 to <18 years of age and boys from 10 to 12 years of age
 - $\circ~$ eGFR (mL/min/1.73 m²) = (0.70 \times height in cm) / serum creatinine in mg/dL for boys from 13 to <18 years of age

Laboratory Test	Parameter for ANY value and LAST value		
Chemistry			
	Absolute Value: >3X ULN		
ALT	Absolute Value: >5X ULN		
	Absolute Value: >8X ULN		
	Absolute Value: >3X ULN		
AST	Absolute Value: >5X ULN		
	Absolute Value: >8X ULN		
ALT >3X ULN and Tbili >2X	Composite: ALT >3X ULN and Tbili >2X ULN [with the Tbili elevation		
ULN	>2 X ULN within 30 days of the ALT elevation >3x ULN]		
AST >3X ULN and Tbili >2X	Composite: AST >3X ULN and Tbili >2X ULN [with the Tbili elevation		
ULN	>2 X ULN within 30 days of the AST elevation >3x ULN]		
Bilirubin	Composite: >ULN and >25% increase from BL		
	Absolute Value: >2X ULN		
Bicarbonate	Absolute Value: <16 mEq/L		
Calcium	Composite: >ULN and >10% increase from BL		
Magnesium	Composite: >ULN and >25% increase from BL		
Phosphorus Composite: >ULN and >25% increase from BL			
Potassium	Composite: <lln and="">15% decrease from BL</lln>		
	Composite: >ULN and >15% increase from BL		
	Absolute Value: $\geq 6.5 \text{ mEq/L}$		
Sodium	Composite: <lln and="" decrease="">5 mEq/L or more from BL</lln>		
	Composite: >ULN and increase>5 mEq/L or more from BL		
Urate	Composite: <lln and="">25% decrease from BL</lln>		
Hematology			
Hemoglobin	Change: $\geq 2 \text{ g/dL}$ decrease from BL		
	Change: $\geq 2 \text{ g/dL}$ increase from BL		
Vital signs			
Pulse	Absolute Value: ≤50 beats per minute		
	Absolute Value: ≥ 100 beats per minute		
Systolic Blood Pressure	Composite: ≥20 mm Hg decrease from BL and ≤90 mm Hg		
	Composite: ≥ 20 mm Hg increase from BL and ≥ 160 mm Hg		
Diastolic Blood Pressure	Composite: ≥ 15 mm Hg decrease from BL and ≤ 50 mm Hg		
	Composite: ≥15 mm Hg increase from BL and ≥100 mm Hg		

Attachment 4: Criteria for Pre-defined Limit of Change (PDLC) and Abnormal Values

ULN = Upper Limit of Normal; LLN = Lower Limit of Normal; BL = Baseline
